An ADAPT4U Smart Phone App has been created for study participants who have an Android phone and are participating in the ADAPT4U study. This App is free by downloading from the App store and will be used voluntarily by study participants. Study participants are given a username and password to access the App. This information is de-identified to the engineer managing the App. Only research staff will have access to identifying information and data collected through the App. When study participants log in they are asked to give consent to their data being collected by research staff and if they agree, to allow access to their App usage data for uploading to the University of Minnesota's server. If study participants do not agree to this, then the data will be uploaded to the University of Minnesota's server when their phone becomes connected to WiFi. The App has observing exercises, already presented in the ADAPT4U curriculum that can be used individually for home practice. They are: Mindful Eating, Ten Deep Breaths, Sitting Observing, Body Scan, Notice 5 Things, Drop Anchor, Leaves on A Stream, Bell Ringing, Hexaflexercise, Wisdom, Loving Kindness, Self-Compassion, and Stretching.

To begin, study participants select the observing activity they want to practice. The App collects data on three questions before study participants begin the observing activity. They are: (1) How do you feel right now, (2) I argued or had conflict with my children or spouse in the past 6 hours, and (3) How much awake time have you spent with your children today so far. Study participants practice the observing activity by listening to the guided audio and/or viewing still pictures. After completing the activity they answer a final question (How do you feel right now?). Data is tracked regarding selected activities, frequency of practice, and responses to the pre and post questions. Study participants that use the App will be put into a monthly drawing for a \$50 gift card. The greater the usage, the more chances they have to win the gift card.

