- Potential risk #1 (discomfort with assessment procedures) and #2 (discomfort in disclosing sensitive information): Safeguards. Participants may choose not to answer questions or not to participate in particular assessment components. Participants have the right to withdraw from this program at any time. All research staff receives training in building rapport with participants and skillful interviewing in order to minimize discomfort and embarrassment. Each study participant receives a verbal and written description of the study. If a staff member determines that a participant's reading skills are limited, all materials will be presented verbally and questionnaires will be administered as an interview. Informed consent is received from the legal guardian(s) of all children participating in the study and children will be asked to assent through a Child Assent form. Participants are advised of their right to withdraw from the project at any time. Experienced research staff members are available at all points of the study process to answer questions and to make the data collection as easy as possible for families.
- Potential risk #3 (violation of confidentiality in accordance with mandatory reporting requirements): Safeguards. To prevent violation of confidentiality, reporting requirements are limited to the mandatory nature of these requirements. Participants are informed verbally and in the consent document that professional staff are required by law to report to the appropriate authorities any danger of serious physical harm to the child, physical injury to any child caused by anything other than accidental means, or any case where the professional suspects a child is being neglected. The consent document also states that staff will inform parents or guardians if, in the judgment of professional staff, their child (under age 18) is in imminent danger of attempting to kill him or herself.

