- Potential risk #4 (violation of confidentiality): Safeguards. Extensive procedures are in place to prevent confidentiality violation and errors resulting from data processing. We will complete and submit an application for a Certificate of Confidentiality to provide further protection of our study participants and our data. Participants are assigned a coded identification number that is used on all data collection measures. Identifying information necessary for participant contact, such as names, addresses, and telephone numbers are kept in locked filing cabinets or in our secure participant database. Access to the online database is restricted to those with valid usernames and passwords and limited to those staff members whose jobs require use of this information for contacting participants. Individuals using this database receive unique and identifiable usernames and passwords. Relational database passwords must be changed on a regular basis. All staff members are required to close password-protected applications or lock their workstations when they are away from their desks.

PROTOCOL TITLE: Comparing Web, Group, and Telehealth Formats of a Military Parenting Program

VERSION DATE: May 4, 2018

During data analysis all identifying information, with the exception of the participant identification number is removed from the data. No information about identities of the study participants will be published or presented at conferences.

- Potential risk #5 (misunderstanding regarding the use of the research data):
Safeguards. Prior to participating in the study, all participants, including children, will read or have read to them a detailed consent or, for children an assent form, described in the Recruitment and Informed Consent section above. Participants will only be asked to sign the consent form after all of their questions and concerns have been addressed to their satisfaction. In addition to explaining the assessment procedures, all potential uses of the collected data, and confidentiality procedures, the consent forms emphasize that participation is completely voluntary, and participants have the right to withdraw from the study at any time. To avoid feelings of coercion, it will be made clear that participation in the study is completely voluntary.

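### As written, the App log-in rule uploads data from users who agree and from users who do not, so a refusal has no effect and conflicts with the protocol's voluntariness safeguard

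*Protocol*

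**What the plan says.** The App is described in Protocol section 5.2 (Study Procedures), after the measures. It is an optional home-practice aid for participants with an Android phone and "will be used voluntarily by study participants".

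At log-in, users are "asked to give consent to their data being collected by research staff and if they agree, to allow access to their App usage data" so that it can be uploaded to the university server. The next sentence gives the alternative: "If study participants do not agree to this, then the data will be uploaded to the University of Minnesota's server". The condition attached is timing, the data reaching the "server when their phone becomes connected to WiFi".

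On content, the section states: "Data is tracked regarding selected activities, frequency of practice, and responses to the pre and post questions". The questions before practice cover current mood, recent conflict with children or spouse, and waking time spent with the children; the mood question is repeated afterwards. On access: "Only research staff will have access to identifying information and data collected through the App". The engineer who manages the App sees de-identified information only.

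Section 14.1 (Foreseeable Risks) sets out the safeguards. Under potential risks #1 and #2, on discomfort with assessment and disclosure: "Participants may choose not to answer questions or not to participate in particular assessment components". Under potential risk #5, on misunderstanding about the use of research data, the protocol relies on detailed consent and assent forms and adds that "it will be made clear that participation in the study is completely voluntary".

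**The concern.** A consent request has meaning only if the two answers lead to different outcomes. Here the stated consequence of not agreeing is the one that the participant was asked to permit: transfer of the data to the study's server. Only its timing is described differently.

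What is at stake is how participants are treated. The records include mood and self-reported family conflict, and research staff have both these data and the information that identifies the user. If the sentence is implemented literally, the study acquires such records from people who were asked and said no. Any later descriptive use of App data would then rest on records whose consent status is in doubt.

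**Working it through.** No arithmetic applies: the plan gives no figure on this point and none depends on it. The check is to trace the branches and compare them with the rest of the protocol.

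**1. Branches at log-in (section 5.2).**
- The user agrees to collection and to upload access: data are uploaded.
- The user does not agree: data are uploaded when the phone is on WiFi.
- No third branch is described in which the data stay on the phone.

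**2. What the word *this* can refer to.** It could point to either of the two permissions, or be a slip for a question about timing.
- *Consent to collection.* People who refuse collection then have their data collected. The refusal is not honoured.
- *Upload access only*, a permission put to people who have already agreed to collection. People who refuse upload then have their data uploaded. The refusal is again not honoured.
- *Timing only*, meaning upload now or wait for WiFi. The rule would then be harmless for people who consent. But the sentence before it asks about collection and access and does not mention mobile data or timing, and the protocol would say nothing about what happens when someone refuses collection.

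The text needs correction on all three readings. The first two override a stated choice; the third leaves refusal of collection without a rule.

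**3. Comparison with the voluntariness text (section 14.1).** The safeguard under risk #5 is that participation is voluntary and that the uses of the data are explained. A log-in question whose negative answer still leads to upload does not fit that. The right to decline under risks #1 and #2 points the same way but is weaker support: it concerns assessment components, whereas the App is a practice tool and does not appear in the schedule of measures at the end of the protocol.

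**4. Comparison with how refusal is treated elsewhere.** Section 13.2 says that data already collected from someone who withdraws voluntarily will not be analysed. Section 13.3 lets people withdrawn involuntarily ask that their data not be used. An explicit refusal counts in both places; the App rule is out of line with them.

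**5. Comparison with the confidentiality rules.** Sections 14.1 (risk #4) and 18.1 call for coded identifiers, restricted access, separate databases and no release of identifying records without written permission. Upload to the study's own server, open to research staff only, breaks none of these. The conflict is with consent and voluntariness.

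**6. Effect on the statistics.** App data appear in no hypothesis, efficacy model or power statement in sections 1.1, 17.1 or 17.2. No sample size, error rate or efficacy estimate changes.

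**The case against.** The strongest defence is that this is loose drafting. The permission to upload is put to people who have already agreed to collection, the disputed sentence follows directly on it, and the only condition it adds is WiFi. A choice between immediate and WiFi-only transfer fits that sequence. Use of the App is also voluntary, so anyone unwilling to share data can leave it alone.

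Part of this stands. The intention may well have been deferral, and the protocol alone cannot show that people who refused collection have had data taken. But the benign reading still leaves refusal of collection without a path. The option of not using the App limits the exposure without giving effect to the answer of someone who opens it and declines.

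A reader might infer more than the document supports:
- *That confidentiality is breached.* The access, coding and release rules are all compatible with the upload.
- *That confidentiality and misunderstanding about data use are the study's main risks.* Section 14.1 lists five potential risks and does not rank them.
- *That a reportable consent deviation has occurred.* Following the protocol is not a deviation from it, and whether it would breach the consent depends on consent wording that is not at hand.
- *That data from people who declined would be mixed in without a marker.* The protocol does not say whether the log-in choice is recorded.
- *That the number of families can be estimated.* There are no figures for App uptake or refusal, so any number would be the product of two guesses.

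**Conclusion.** The point holds as a defect in a stated rule: in section 5.2 every described answer at App log-in ends in upload, so refusing collection or upload access has no effect. This conflicts with the voluntariness safeguard under risk #5 and, less directly, with the right to decline under risks #1 and #2.

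Its reach is every App user who declines; how many that is cannot be derived from the protocol. The conclusion rests on the plain wording and does not require a choice among the readings of the sentence, because none of them leaves a workable refusal path. It does not rest on any claim that data have in fact been taken from people who refused.

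The correction should be made to protect participants. It has no bearing on the validity of the trial's efficacy results.

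**What to change.** Rewrite the App paragraph in section 5.2 so that two questions are kept apart:

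1. *Consent to research collection.* If refused, no App responses or usage data are uploaded, and the exercises remain available.
2. *Upload timing, for people who consent only.* Immediate upload, or upload only on WiFi.

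Record the consent choice with the App data. Bring the App log-in text and consent wording into line with section 5.2 and with the voluntariness text in section 14.1. Check whether any data were uploaded from people who refused collection; if so, exclude and delete them. If only deferral to WiFi was ever meant, corrected wording plus a stated refusal path resolves the matter.

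The cost is a change to protocol and consent wording, a small App setting, and slightly less App usage data. One practical consequence needs a sentence: section 5.2 gives heavier users more chances in the monthly gift-card drawing, so the protocol should say how people who decline upload are treated there.

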6.0 Data Banking – NA

7.0 Sharing of Results with Participants – NA

8.0 Study Duration

8.1 Describe:

- Study participants can expect to be involved in the study for 2 years.
- December 31, 2017
- May 31, 2019

9.0 Study Population

9.1 Inclusion Criteria:

Inclusion criteria are: (a) one parent has returned from deployment to OIF or OEF or stateside deployment in support of the Global War On Terrorism, (b) at least one child ages 5-12 in their custody and living with parent(s) in the home, and (c) high speed internet access at home (a MN study indicates that 97% deployed families have internet, with 70% using internet daily; Sayer et al., 2009). We will include both single-and two-parent families, as well as families where care is shared between non-partnered adults (e.g. grandparent and mother), and will control for relationship status in analyses. Participants must live within an hour's

PROTOCOL TITLE: Comparing Web, Group, and Telehealth Formats of a Military

Parenting Program

VERSION DATE: May 4, 2018

travel time of Grand Rapids, Kalamazoo, Battle Creek or Selfridge, MI, the Twin Cities Metro area, St. Cloud or Duluth, MN, agree to randomization, and indicate willingness to interact with study materials and complete assessment batteries.

9.2 Exclusion Criteria:

Exclusion criteria include: (a) active psychosis, (b) an open child protection case for abuse or neglect in the family, (c) a serious child mental health diagnosis, (d) families who piloted material or participated in or are currently participating in the original ADAPT RCT. MN ARNG data indicate that fewer than 10% families would be excluded based on a-c, above (personal correspondence, [name]).

There is no reason to exclude women of childbearing potential. There will be no exclusion of racial or ethnic groups.

9.3 Screening:

Potential participants will be asked to take an online eligibility survey that will screen for inclusion criteria.

10.0 Vulnerable Populations

10.1 Vulnerable Populations:

- Children
- Pregnant women/Fetuses/Neonates
- Prisoners
- Adults lacking capacity to consent and/or adults with diminished capacity to consent, including, but not limited to, those with acute medical conditions, psychiatric disorders, neurologic disorders, developmental disorders, and behavioral disorders
- Non-English speakers
- Those unable to read (illiterate)
- Employees of the researcher
- Students of the researcher
- None of the above

10.2 Adults lacking capacity to consent and/or adults with diminished capacity to consent: NA

10.3 Additional Safeguards:

Child Participants: The informed consent process for child participation will be conducted during the in-home assessment process. The study, procedures, and tasks of the study will be explained to both the parent and the child. Both child assent and parental consent forms will be presented to the family and explained. The research staff conducting the informed consent process will ask each child to explain the study process in their own words to assure that they understand what is being asked of them and what they will be asked to do (e.g. answer questions, play a game with their parents, be willing to be video-taped while playing the game). Research staff will ask both the parent and child, separately and directly,

PROTOCOL TITLE: Comparing Web, Group, and Telehealth Formats of a Military

Parenting Program

VERSION DATE: May 4, 2018

if they have any questions or concerns about the study. It will be stated very directly to the child that no one will be angry or upset with them if they decide not to participate in the study and that they can change their mind or ask more questions at any time during the study. Once the research staff has been able to ascertain that both the child and the parent understand the procedures of the study and what the child will be asked to do, written signatures will be requested from the parent and child on both the Child Assent form and the Parental Consent form.

Families will be provided with a copy of all consent forms they have signed.

The following consent forms will be obtained from participants:

- a. Adult consent for participation in the clinical study (all family adults screened for participation in the clinical study)
- b. Parental consent for child's participation in baseline and follow-up assessments (all parents of children in the study)
- c. Child Assent Form for participation in baseline and follow-up assessments (all children in study)
- d. Adult Consent to release observational assessment video data (all families)
- e. Teacher consent to participate in study (teachers of targeted child only)

11.0 Number of Participants

11.1 Number of Participants to be Consented: 630

12.0 Recruitment Methods

12.1 Recruitment Process:

Recruitment flyers promoting the study will be distributed to our partners (NG, VA, M-SPAN). In addition, the PI has been invited by the MN ARNG to present at reintegration workshops which are mandatory for all soldiers returning from OEF/OIF deployment, and flyers will be handed out there. Flyers provide the phone and email contact information for the researchers, and the study site URL. The website guides parents to a brief explanation of the project, and a description of project confidentiality and its limits. Refer a friend post cards will be distributed to previous ADAPT study participants and current participants (as recruitment occurs). A recruitment/outreach booth will be set-up at the MN State Fair on Military Appreciation Day.

Interested participants will be directed to an anonymous online screening instrument. This screen determines eligibility based on the above stated inclusion and exclusion criteria. Eligible participants will next complete a brief contact information form, followed by an online informed consent that will provide information about study risks, benefits and about the possibility of being randomly assigned to either an intervention (E) group or SAU comparison group. In reintegrating families with two at-home participating parents/caregivers, each will complete a separate informed consent.

PROTOCOL TITLE: Comparing Web, Group, and Telehealth Formats of a Military Parenting Program

VERSION DATE: May 4, 2018

Eligible participants will next complete a brief contact information form, followed by an online informed consent providing information about study risks, benefits and the possibility of being randomly assigned to one of three intervention conditions: group-based ADAPT (G), web-only/self-directed ADAPT (W), or individualized web-facilitated ADAPT (F). In reintegrating families with two at-home participating parents/caregivers, each will complete a separate informed consent.

Consenting participants will be provided a contact number to speak to the PI or study coordinator with questions. Families requesting a telephone screening will be asked for verbal consent for the team to maintain contact through reminder emails and phone calls as needed to complete informed consent and BL online assessments. Informed consent may also be completed at the in-home assessment.

Participants who submit informed consents will automatically be directed to log in to the BL assessment by providing their email and creating a password.

Attrition and Enhancing retention: We expect attrition to be 5-20%, based on current study data, and have calculated power accordingly.

Assessors in all conditions will use retention tools successful in this and other stressed populations: 1) Families give contact information for themselves and 3 friends/family members. 2) Parents receive pre-stamped cards with study address and receive \$20 for providing their new address. 3) We provide study updates in newsletters, and bi-yearly mailings. We will use evidence-based strategies for enhancing retention. To encourage assessment completion we will compensate participants. To enhance participation in group (G) activities, we will hold two drawings at each session: group start for timeliness, group end for home practice completers, for small prizes (e.g. chocolate; journals; stress balls). In W and F conditions, participants will receive small online gift cards for participation and online completion (\$10 per module completed). We will hold groups at convenient times for families (e.g. early evening hours), include meals for participants, and onsite childcare. Transportation stipends and free parking will be provided. If increasing recruitment numbers become a challenge, we will offer a refer a friend bonus of a \$5 gift card and/or put the referrer and referee into a drawing for a \$100 gift card.

12.2 Source of Participants:

Military (current or former) and their families who self-identify and live in within an hour's travel time of Grand Rapids, Kalamazoo, Battle Creek or Selfridge, MI, the Twin Cities Metro area, St. Cloud or Duluth, MN.

12.3 Identification of Potential Participants:

Participants will self-identify in response to media and local installation publicity, attendance at outreach/unit/family events, and through contact with service providers such as chaplains, military and family life consultants, and so on. Initial

PROTOCOL TITLE: Comparing Web, Group, and Telehealth Formats of a Military Parenting Program

VERSION DATE: May 4, 2018

contact will be made by site coordinator on each installation only after participants express interest and provide their contact information.

12.4 Recruitment Materials:

Primary recruitment materials will be flyers. Flyers will be available through service providers and military partners, at installation events and on social media. Flyers can also be send as email attachment or embedded as a picture into communications.

12.5 Payment:

Subjects will be compensated utilizing Target (or similar) gift cards for assessment activities as follows:

Effectiveness trial participants (N=360 families) will be paid \$50 for in-home assessments at baseline and 12 months, and \$100 at 24 months post-baseline; children will be provided a small gift valued at \$5. Each adult completing an online assessment (at baseline, 6, 12, 24 months), up to 2 adults per family, will be compensated \$25 per assessment. 2 parent families who complete all surveys and in-home assessments can make up to \$400 and 1 parent families can make up to \$300.

Families randomly assigned to the face-to-face group intervention (N= 120 families) will be compensated \$10 for each group session attended to offset travel costs, as well as an additional \$5 when they complete at least two online assignments per module (14 maximum). Small prizes will be distributed at each group session for attendance and homework completion. Full participation would entail 14 sessions and result in a \$210 incentive per family.

Families randomly assigned to the online-facilitated intervention (N= 120 families) will be compensated \$5 per one-hour session with a facilitator, as well as an additional \$5 when they complete at least two online assignments per module (140 maximum). Full participation would entail 140 sessions and result in a \$1400 incentive per family.

Families randomly assigned to the online-only intervention (N= 120 families) will be compensated \$5 for each parent who completes at least two online assignments per module (140 maximum). Full participation would entail 140 sessions for each parent and result in a \$1400 incentive per family.

2 parent families have the potential to be compensated up to \$610, and single parent families have the potential to be compensated up to \$510.

Teachers will be compensated \$15 for completing yearly assessments (at baseline, 12, and 24 months)

Compensation will be provided along the way as subjects complete each in-home assessment and online surveys, and each week as they complete either the in-person groups or the online modules.

PROTOCOL TITLE: Comparing Web, Group, and Telehealth Formats of a Military Parenting Program

VERSION DATE: May 4, 2018

Subjects will be compensated for all of the assessments, surveys, and group sessions they attend.

